**Acute Pain:**

**PROMIS Numeric Rating Scale - Pain Intensity** - An 11-point numeric scale ranging from 0 (no pain) to 10 (worst possible pain) for average pain. This survey will be administered to all participants at baseline, 10 days, 1-month, 3-months, and 6-months post-surgery.

**PROMIS pain intensity scale** – A participant completed 3-question survey of average pain over the last 7 days, worst pain over the last 7 days, and current pain. Each question is on a 1-5 integer scale, the higher the value, the more intense the pain. This survey will be administered to all participants at baseline, 10 days, 1-month, 3-months, and 6-months post-surgery.

**Opioid consumption questionnaire** – A participant completed survey of pain prescription medication consumption, including the type of opioid pain medication, number of pills dispensed, if a refill has been obtained, and the number of pills left for each opioid pain medication selected. This survey will be administered to all participants at 10 days and 1-month post-surgery.

**PROMIS prescription medication mis-use scale** - A participant completed survey of prescription medication misuse over the past 3 months. The survey is comprised of 7 questions on a 5-point ordinal scale of never/rarely/sometimes/frequently/almost always or not at all/a little bit/somewhat/quite a bit/very much[33]. This survey will be administered at baseline, 3-months, and 6-months post-surgery.

**PROMIS Item Bank v2.0 Mobility** – A participant completed survey of the participant's level of difficulty in completing different physical activities such as standing unassisted, walking, and sprinting or activities that their health currently limits. The survey is comprised of 15 questions, each answered on a 5-point scale ranging from without difficulty to unable to do, or not at all through cannot do[34]. This survey will be administered at baseline, 10 days, 1-month, 3-months, and 6-months post-surgery to the adult participants.

**PROMIS Pediatric Mobility – Short Form 8a** – A participant completed 8 item survey of difficulty in completing different physical activities such as getting up from the floor, standing on tiptoes, and ability to do sports and exercises that their peers can complete [35]. The survey will be administered at baseline, 10 days, 1-month, 3-months, and 6-months post-surgery to the pediatric participants.

**Acute pain specific health care utilization** – A participant completed survey of hospital length of stay for the surgical admission, administered at 10 days post-surgery.

**Opioid side effects** – A participant completed survey of common opioid side effects experienced and the extent to which those side effects bothered the participant. This survey will be administered at baseline, 10 days, 1-month, 3-months, and 6-months post-surgery.

**Opioid persistence** - Whether or not the participant had an opioid prescription refill 90 – 180 days post-surgery. This survey will be administered to participants at 6 months post-surgery.

**Chronic Pain:**

**PROMIS pain intensity scale** – A participant completed 3-question survey of average pain over the last 7 days, worst pain over the last 7 days, and current pain. Each question is on a 1-5 integer scale, the

higher the value, the more intense the pain. This survey will be administered at baseline, 1 month, 3 months, and 6 months post return of results.

*PROMIS prescription pain medication mis-use scale* - A participant completed survey of prescription medication misuse over the past 30 days. The survey is comprised of 7 questions on a 5-point ordinal scale of never/rarely/sometimes/frequently/almost always or not at all/a little bit/somewhat/quite a bit/very much[33]. This survey will be administered at baseline, 3 months, and 6 months post return of results.

*PROMIS emotional distress depression 8b survey* - A participant completed eight question survey assessing frequency of depression symptoms over the past 7 days[36]. This survey will be administered at baseline, 1 month, 3 months, and 6 months post return of results to the adult participants.

*Opioid side effects* – A participant completed survey of common opioid side effects experienced and the extent to which those side effects bothered the participant. This survey will be administered at baseline, 3 months, and 6 months post return of results to the adult participants.

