#### **Depression:**

*PROMIS emotional distress depression 8b survey* - A participant completed eight question survey assessing frequency of depression symptoms over the past 7 days[36]. This survey will be administered at baseline, 1 month, 3 months, and 6 months post return of results to the adult participants.

*PROMIS Pediatric Depressive Symptoms Short Form 8a*- A pediatric (ages 8-17 years) participant completed eight question survey assessing frequency of depression symptoms over the past 7 days[37]. This survey will be administered at baseline, 3 months, and 6 months post return of results to the pediatric study participants .

*Patient Health Questionnaire-8* – An 8 item survey completed by the participant assessing depression symptoms over the last two weeks. This survey will be administered at baseline, 3 months, and 6 months post return of results[38].

*Antidepressant side effects* – A participant completed survey of relevant antidepressant side effects. This survey will be administered at baseline, 1 month, 3 months, and 6 months post return of results.

*Voils Medication Adherence* - A participant completed three question survey, 5-point scale survey assessing participant medication adherence[39]. This survey will be administered to depression trial participants at baseline, 1 month, 3-months and 6 months post return of results.

All of the PROMIS® surveys can be found online[40].

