**Table 8. Data collection schedule**

### Data collection schedule, method of data collection, and timing

Outcome	Data source/instrument	Baseline	10 d ± 3 d	1 mo. ± 7 d	3 mo. ± 14 d	6 mo. ± 14 d
Pain Assessments						
Pain intensity	PROMIS Pain intensity scales	AP, CP	AP	AP, CP	AP, CP*	AP, CP
Pain intensity	PROMIS Numeric Rating Scale - Pain Intensity (NPRS)	AP	AP*	AP	AP	AP
Daily opioid dose & type of opioid use	Average daily mg morphine equivalents (MED) since discharge use of opioids: tramadol/ codeine vs others		AP*	AP		
Opioid use disorder	PROMIS - Prescription pain medication misuse subscale	AP, CP			AP, CP	AP, CP
Mobility	PROMIS mobility	AP	AP	AP	AP	AP
Depression Assessments						
Depressive state	PROMIS Emotional Distress - Depression 8b survey	CP, D		CP, D	CP, D*	CP, D
Depressive state	Patient Health Questionnaire-8 depression scale	D			D	D
Participant Medications						
Assessment of prescriptions	Custom survey/EHR	AP, CP, D	AP		CP, D	
Assessment of filled prescriptions	Medicaid and Medicare billing records for 12 months prior to time 0 through 6 months after time 0		AP, CP, D			

Adherence	Voils Medication Adherence		D		D	D	D
SSRI AE Survey	Custom survey		D		D	D	D
Opioid side effect survey	Adapted medication side effect survey (SPACE)		AP, CP	AP	AP, CP	AP, CP	AP, CP
Opioid persistence	Custom survey						AP
Participant Actions							
Interaction with provider	Participant visits				CP, D		
Interaction with test result	Custom survey						AP, CP, D
Quality of life and well being							
Past Medical History	Participant visits/custom survey		AP, CP, D				
Well-being	PROMIS43/PROMIS Peds37		AP, CP, D		AP, CP, D	AP, CP, D	AP, CP, D
Healthcare Utilization and Costs							
Medicare/Medicaid billing records	Medicaid and Medicare billing records for 12 months prior to time 0 through 6 months after time 0				AP, CP, D		
LoS	LoS for index admission			AP			
ED/urgent care & inpatient visits	Participant reported visits				AP, CP, D	AP, CP, D	AP, CP, D
Outpatient visits	Participant reported primary care & pain clinic visits				AP, CP, D	AP, CP, D	AP, CP, D
Outpatient visits	Long-term care or in-patient rehab days, home healthcare days				AP	AP	AP
Productively Loss	Survey of lost work time and income				AP, CP, D	AP, CP, D	AP, CP, D

Abbreviations: CP – chronic pain, AP – acute post-surgical pain, D-depression, ED – emergency department, EHR – electronic health record; LoS – length of stay; PT – physical therapy

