#### Depression

To determine the effect of genotype-guided drug therapy on depression symptoms in depression

participants, we will conduct a subset analysis comparing change in depression T-scores from baseline to 3-month follow-up in the Intervention group subset with either CYP2D6 PM or UM or CYP2C19 PM, RM or UM phenotypes to the Control group subset with CYP2D6 PM or UM or CYP2C19 PM, RM, or UM phenotypes. Participants that have other CYP2D6 or CYP2C19 phenotypes will not be included. Pediatric depression T-scores will be transformed to the adult scale using a published crosswalk for a combined analysis. The baseline to 3-month change in depression T-scores of the Intervention CYP2D6 PM/UM or CYP2C19 PM/RM/UM group will be compared to the baseline to 3-month change in depression T-scores of the Control CYP2D6 PM/UM or CYP2C19 PM/RM/UM subgroup using a two-sided two-sample t-test with a type 1 error of 0.049. This primary analysis will be conducted according to a modified intent-to-treat design, with participants analyzed and endpoints attributed according to the treatment arm to which the participants were randomized, regardless of subsequent crossover or post-randomization medical care.

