#### Depression

**Trends in endpoints.** In addition to the primary and secondary endpoints described above, we will compare the time trends in the endpoint depression symptom scores at baseline, 1, 3, and 6 months among the CYP2D6 PM or UM or CYP2C19 UM, RM or PM subgroup, using a repeated-measures mixed effect model. Since participants are randomized to Intervention and Control groups and not to the CYP2D6 PM or UM or CYP2C19 UM, RM or PM subgroup within Intervention and Control groups, there could be important differences in baseline characteristics between the two groups. For these

reasons, we will conduct covariate-adjusted repeated measures mixed models that will account for differences in baseline characteristics that differ between the Intervention – CYP2D6 PM or UM or CYP2C19 UM, RM or PM subgroup and the Control – CYP2D6 PM or UM or CYP2C19 UM, RM or PM subgroup. Potential baseline characteristics may include age, sex, income, education, insurance, medical conditions. We will select the appropriate covariance matrix (e.g. compound symmetry, autoregressive, unstructured, or other covariance structure) based on the data.

*Difference within the NM group.* In the control arm participants, we will compare depression scores and depression control in participants with a CYP2D6 activity score  $>0.75 - 1$  to participants with an activity scores  $>1-2$  using a two-sided two-sample t-test or Mann Whitney test, as appropriate, with a type 1 error of 0.05. Additionally, we will use linear regression to adjust for differences in baseline characteristics

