### **10.8 Handling of Missing Data**

For all primary and secondary statistical analyses described above, multiple imputation will be used for all missing values except those due to participant death. To ensure that the missing at random assumption for multiple imputation is valid, we will compare baseline pain or depression scores and other patient characteristics in those lost to follow up to participants retained on their randomization assignment. We will also do sensitivity analyses where we compare results obtained with multiple imputation to those obtained without imputation. Missing values due to death will not be imputed and will therefore not be included in the analyses. For exploratory repeated measures analyses, missing data are easily handled as long as the missing at random assumption is valid. However, the missing at random assumption cannot be tested. Accordingly, for exploratory analyses using repeated measures mixed models, we will also conduct a sensitivity analysis where missing values are imputed using multiple imputation. The results with and without multiple imputation will be compared. More complete details of the handling of missing values under different circumstances will be described in the SAP.

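### Section 7.3 and Table 8 disagree on the 1-month opioid side-effect survey in chronic pain, and Section 7.3 schedules no 1-month pediatric 8a although the 10.6 trend model uses a 1-month depression score

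*Combined protocol and SAP*

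**What the plan says.** **Chronic pain, opioid side effects.** Section 7.3 (Chronic Pain) has this survey "administered at baseline, 3 months, and 6 months post return of results to the adult participants". The opioid side-effect row of Table 8 has entries in all five columns: acute and chronic pain at baseline, acute pain alone at 10 days, and both trials at 1, 3 and 6 months. Section 8.1 says that side effects are collected in the baseline and follow-up surveys and names no month. The opening of 7.3 lists 1 month among the follow-up times for chronic pain and depression.

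**Depression score.** For the adult 8b, Section 7.3 (Depression) says: "This survey will be administered at baseline, 1 month, 3 months, and 6 months post return of results to the adult participants". For the pediatric 8a it says: "This survey will be administered at baseline, 3 months, and 6 months post return of results to the pediatric study participants". In Table 8 the depression trial is marked at baseline, 1, 3 and 6 months against the "PROMIS Emotional Distress - Depression 8b survey"; the pediatric form has no row.

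**Analysis.** For the primary analysis, Section 10.4 states: "Pediatric depression T-scores will be transformed to the adult scale using a published crosswalk for a combined analysis". The exploratory trend analysis in Section 10.6 then compares "time trends in the endpoint depression symptom scores at baseline, 1, 3, and 6 months" in the actionable subgroup, with no exception for children. For exploratory mixed models, Section 10.8 adds that "we will also conduct a sensitivity analysis where missing values are imputed using multiple imputation".

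**The concern.** The side-effect survey is the chronic pain trial's direct participant report of opioid tolerability, and the intervention advises prescribers to avoid certain opioids in actionable phenotypes. Side effects soon after a change of medication are best seen at the first follow-up. If sites or the call center work from 7.3, the first reading comes at about 3 months, when early symptoms may have resolved or may already have led to another change. If some work from 7.3 and others from Table 8, the 1-month data will be uneven.

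In depression, the trend model needs a score at a visit where, under 7.3, no child completes the form behind the pediatric primary endpoint. The 1-month contrast between arms would then rest on adults and on the assumption that their time course applies to children, yet be reported for all ages. The imputation sensitivity analysis would fill in every child's 1-month 8a without one observed pediatric 8a at that visit.

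**Working it through.** No sample size, power or alpha figure is involved. The check is a comparison of time points (months after time 0, with 0 for baseline), followed by one calculation of visit windows.

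| Measure | Section 7.3 | Table 8 | Use in 10.6 |
|---|---|---|---|
| Opioid side effects, chronic pain | 0, 3, 6 | 0, 1, 3, 6 | descriptive summary |
| Opioid side effects, acute pain | 0, 10 days, 1, 3, 6 | 0, 10 days, 1, 3, 6 | descriptive summary |
| Antidepressant side effects | 0, 1, 3, 6 | 0, 1, 3, 6 | descriptive summary |
| Adult 8b, depression trial | 0, 1, 3, 6 | 0, 1, 3, 6 | trend model at 0, 1, 3, 6 |
| Pediatric 8a, depression trial | 0, 3, 6 | no row of its own | trend model at 0, 1, 3, 6 |
| PROMIS pediatrics 37, depression trial | 0, 1, 3, 6 | 0, 1, 3, 6 | not named in the trend model |
| PHQ-8 | 0, 3, 6 | 0, 3, 6 | not named in the trend model |

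1. *Chronic pain side effects.* There are three time points in 7.3 and four in Table 8; the unmatched one is 1 month. The five filled cells of the Table 8 row map to its five column headings, so the entry at 1 month is not an artefact of a broken table. Both texts are current. The acute pain and antidepressant surveys both include 1 month, and 8.1 read with the opening of 7.3 points the same way. The chronic pain sentence in 7.3 is the one that stands apart.

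2. *Size of the delay.* Table 8 gives windows of ±7 days at 1 month and ±14 days at 3 months. Taking a month as 30 days:
   - under Table 8, the first reading falls at 30 ± 7 = day 23 to 37;
   - under 7.3, it falls at 90 ± 14 = day 76 to 104;
   - the target dates differ by 90 − 30 = 60 days.

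3. *Pediatric 8a.* There are three time points in 7.3 and four in the trend model; again 1 month is unmatched. Under 7.3, all children lack the 1-month 8a by design. The PHQ-8 cannot stand in, because it too has no 1-month reading. The PROMIS pediatrics 37 has a depression sub-domain and is given at 1 month, but no section says that its score may replace the 8a in the model or support its imputation. The documents do not give the share of children in the depression trial, so the weight of this gap in the pooled estimate cannot be calculated.

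4. *What is not touched.* The chronic pain and depression primary endpoints are changes from baseline to 3 months, and both instruments are scheduled at those times. Side effects are not a secondary endpoint in chronic pain (Section 3.2); Section 10.6 summarizes them as counts and percentages.

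**The case against.** A reader might infer that early harm in chronic pain and children's early response in depression go unmeasured, or that 7.3 drops the 1-month visit. The documents do not support this:

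- Section 7.3 keeps the 1-month contact in both trials; it omits one instrument in each.
- Side-effect data at 1 month are lost only if 7.3 is taken to govern over Table 8 and 8.1. Emergency department visits and hospitalizations are collected at 1 month in either case (Section 8.2), although they do not capture the symptoms listed in 8.1, such as nausea, constipation and dizziness.
- Children's depression is measured at 1 month by the PROMIS pediatrics 37 sub-domain. Their antidepressant side effects and adherence are also collected then.
- It is tempting to add that imputation of a missing 3-month 8a is left without any interim information. That is true only of the 8a itself; the sub-domain score could serve as an auxiliary variable, and imputation details are left to the separate SAP.

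Table 8 can also be read more generously. Its depression row carries the primary-endpoint asterisk at 3 months, and that endpoint includes the pediatric form, so the row may be meant to cover both forms. If so, Table 8 schedules the 8a at 1 month and contradicts 7.3 on this instrument as well. Either reading leaves text to reconcile.

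On the statistics, a score missing by age group is not missing because of its value. Age is a listed potential covariate, and randomization is stratified by pediatric or adult status, so the gap should fall on both arms alike. This limits bias in the comparison of arms. It does not supply a 1-month 8a for children, and it does not make an adult-based 1-month contrast an all-age result.

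**Conclusion.** Two scheduling faults stand. First, 7.3 and Table 8 contradict each other on whether chronic pain participants complete the opioid side-effect survey at 1 month, and the surrounding text agrees with Table 8. If 7.3 is followed, the first reading moves from about day 23-37 to about day 76-104, assuming 30-day months and the Table 8 windows. This is a conflict over which passage governs, not an established loss of data. Second, 7.3 provides no 1-month pediatric 8a, and Table 8 names only the adult 8b, although the 10.6 trend model uses depression scores at 1 month for the whole actionable subgroup.

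The reach is limited to descriptive tolerability summaries and an exploratory model; the 3-month primary endpoints are not redefined. This is a minor point, worth correcting because the correction is cheap.

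**What to change.** 1. Reconcile 7.3 with Table 8 so that the chronic pain opioid side-effect survey is collected at the existing 1-month contact. For participants already past that contact without the survey, report the 1-month summary on those observed, with the number observed in each arm.
2. For the pediatric 8a, either add it at the 1-month contact in 7.3 and give it its own row in Table 8, or, where that visit has passed, fit and label the 1-month 8a/8b contrast as adults only and state in 10.8 that children's 1-month 8a scores are not imputed.
3. In the same pass, correct a parallel mismatch: the acute and chronic pain trend models in 10.6 list the opioid misuse score at 1 month, but 7.3 and Table 8 collect it only at baseline, 3 and 6 months.

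The cost is wording in 7.3, Table 8, 10.6 and 10.8, plus one short survey (eight items for children) at a contact where the PROMIS 43 or pediatrics 37 is already completed. Labelling the contrast as adults only adds no data collection.

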#### **Depression:**

*PROMIS emotional distress depression 8b survey* - A participant completed eight question survey assessing frequency of depression symptoms over the past 7 days[36]. This survey will be administered at baseline, 1 month, 3 months, and 6 months post return of results to the adult participants.

*PROMIS Pediatric Depressive Symptoms Short Form 8a*- A pediatric (ages 8-17 years) participant completed eight question survey assessing frequency of depression symptoms over the past 7 days[37]. This survey will be administered at baseline, 3 months, and 6 months post return of results to the pediatric study participants .

*Patient Health Questionnaire-8* – An 8 item survey completed by the participant assessing depression symptoms over the last two weeks. This survey will be administered at baseline, 3 months, and 6 months post return of results[38].

*Antidepressant side effects* – A participant completed survey of relevant antidepressant side effects. This survey will be administered at baseline, 1 month, 3 months, and 6 months post return of results.

*Voils Medication Adherence* - A participant completed three question survey, 5-point scale survey assessing participant medication adherence[39]. This survey will be administered to depression trial participants at baseline, 1 month, 3-months and 6 months post return of results.

All of the PROMIS® surveys can be found online[40].

## 7.4 Specimen Collection

DNA sample collection can be whole blood by venipuncture, saliva, buccal swab, or mouthwash, whichever is most appropriate for the site or study participant preference. The sample collection can occur in person or by mailed kits after consenting.

Once sample collection is completed, participants are randomized to a trial Control or Intervention arm. All DNA sample types and collection processes are detailed in the MOP.

## 7.5 Specimen Transfer and Genetic Testing Procedures

All collected specimens will be clearly marked with two patient identifiers (CLIA requirement). Samples from the Intervention arm participants will be processed, using analytically validated PGx testing procedures (see Table 1 for gene and variant list). For Control arm samples, designated laboratories will either extract DNA after sample receipt, and store the DNA for later analysis or store the sample and extract DNA after the Control participant has completed the 6-month follow-up assessment. After the Control participant has completed the 6-month follow-up assessment, Control Arm samples will be processed using analytically validated procedures. Details of sample storage and transport will be presented in the MOP.

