## 1. PROTOCOL SYNOPSIS

Protocol Title	A Depression and Opioid Pragmatic Trial in Pharmacogenetics ( ADOPT-PGx )
US IND Number	
Grant Number	
Product/Intervention	Immediate vs. delayed pharmacogenetic testing and genotype-guided pain or depression therapy
Objectives	
Acute Pain:
 
 
• To determine the effect of genotype-guided therapy on pain control and use of DEA schedule II opioids in post-surgical participants
 
 
Chronic Pain:
 
 
• To determine the effect of genotype-guided therapy on pain control in chronic pain participants
 
 
Depression:
 
 
• To determine the effect of genotype-guided selection and dosing of antidepressants on control of depression in participants with <math>\geq 3</math> months of depressive symptoms who require new or revised therapy
 
 
All Trials:
 
 
• To determine the effect of genotype-guided therapy for opioids, antidepressants, and optional additional, CPIC gene-drug pairs on overall well-being
 
• To determine the effect of genotype-guided therapy for opioids, antidepressants, and optional additional, CPIC gene-drug pairs on healthcare utilization
 

Study Design	ADOPT PGx is comprised of three separate trials, Acute Pain, Chronic Pain, and Depression. Each trial is a prospective, multicenter, two arm randomized pragmatic trial. For all trials, participants will be randomized in a 1:1 ratio to immediate pharmacogenetic testing and genotype-guided therapy (Intervention arm) or 6-month delayed testing on participants receiving standard care (Control arm). In each trial, the primary outcome comparison will be between the intervention group (i.e. immediate testing) and control group (i.e. delayed testing) in the subset of participants with actionable phenotypes, within each study.

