### **8.4 Early Termination and Participant Discontinuation**

Early termination considerations will generally apply only to emerging issues of major concern, or problems with trial conduct that suggest the trial could not be completed successfully with a reliable conclusion in a feasible time frame.

The site investigator, sponsor or institution may stop involvement of any participant in this research

study at any time without their consent. This may be because the research study is being stopped, the instructions of the study team have not been followed, the investigator believes it is in the participant's best interest, or for any other reason. If specimens or data have been stored as part of the research study, they too may be destroyed without participant consent.

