### **10.3 Population for Analyses**

#### Acute pain

Participants randomized who have an actionable phenotype, specifically participants who are genotypically or pheno-converted CYP2D6 IM or PMs (i.e. CYP2D6 activity score  $\leq 0.75$ ).

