#### Depression

The interim analysis of the depression primary endpoint, depression control at 3 months post return of PGx testing result to providers, will compare the participants with *CYP2D6* PM/UM or *CYP2C19* PM, RM and UM phenotypes in the Control arm to the participants with *CYP2D6* PM/UM or *CYP2C19* PM/RM/UM phenotypes in the intervention arm.

The primary analysis is a modified intent to treat design and the analytical subgroup is defined by the results of the PGx testing. Because the drug metabolizer phenotypes for participants in the Control arm is determined around the time of the 6-month follow up assessments for all trials (Acute Pain, Chronic Pain, and Depression), only participants that have completed their 6-month assessments will be included in the interim analysis. To account for the delays in receiving genetic testing results, the interim analysis will be targeted to occur when approximately 50% of the participants have completed their 6-month assessments. If the interim analysis does not propose stopping for efficacy (p-value  $<0.0003$  and the intervention has the larger reduction in the primary endpoints), then the conditional power to detect a significant result at the end of the trial will be estimated. The conditional power will be presented to the DSMB to facilitate discussion of whether the trial should be stopped for futility.

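### Read literally, section 7.5 genotypes a control only after that participant completes month 6, and the plan does not say how control non-completers are classified for the final primary analysis set

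*Combined protocol and SAP*

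**What the plan says.** - **Sampling (7.4).** DNA is collected before allocation in both arms: "Once sample collection is completed, participants are randomized to a trial Control or Intervention arm".
- **Testing (7.5).** Intervention samples are processed without any follow-up condition. For controls: "After the Control participant has completed the 6-month follow-up assessment, Control Arm samples will be processed using analytically validated procedures". Section 6.6 (Improved drug therapy) also ties recording of a control's genotype to completing the 6-month follow-up.
- **Primary set (10.3).** "Participants randomized who have an actionable phenotype", in parallel wording for the three trials. Completing month 6 is not a condition, and an undetermined phenotype is not mentioned.
- **Primary endpoints (10.4).** SIA score at 10 days (acute pain) and change from baseline to 3 months (chronic pain, depression), analysed by randomised arm as modified intent-to-treat.
- **Interim analysis (10.7).** "only participants that have completed their 6-month assessments will be included in the interim analysis", stated for participants in general and for the interim analysis alone.
- **Missing data (10.8).** "multiple imputation will be used for all missing values except those due to participant death". Whether phenotype, and so membership of the primary set, counts as a missing value is not said.

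**The concern.** Take two participants with the same history: an observed primary endpoint, an actionable genotype, and no 6-month assessment. The one in the intervention arm has a genotype and is in the primary set. The one in the control arm, if 7.5 is followed to the letter, is never genotyped and cannot be placed in it unless classified some other way. The control group would then be conditioned on a post-endpoint event that does not act on the intervention group, and some observed control endpoints would go unused.

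That sits badly with analysis by randomised arm in 10.4, and with section 6.3, which keeps data collected before withdrawal in use. The trial is open label (4.2), so drop-out related to arm or outcome is conceivable, though the documents give no data on it. Section 10.1 recognises the delay in control genotyping for enrolment monitoring, and 10.7 recognises it for the interim analysis. Nothing does so for the final primary analysis.

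**Working it through.** **Plan's own figures.** Two-sided two-sample t-test, alpha 0.049, power 90%, effect sizes 0.375, 0.40 and 0.28 (10.1, Table 9). The exact t-test gives 151.2, 133.0 and 270.4 per arm, which round up to the plan's 152, 134 and 271. Dividing by actionable shares of 18%, 30% and 40%, then by 0.90 (0.90 × 0.93 for acute pain), gives 2,020, 994 and 1,507 randomised, against 2,020, 994 and 1,508 in Table 9.

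**Ceiling on unclassified actionable controls.** Section 10.1 counts people completing all assessments, so the 10% is read here as loss by month 6. Unclassified = completers per arm × 0.10/0.90:

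- acute pain 152/9 = 16.9
- chronic pain 134/9 = 14.9
- depression 271/9 = 30.1

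Two things pull the numbers that matter below these.

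1. *Observed endpoints.* Only controls with an observed primary endpoint lose data. The plan gives no loss curve. If loss were constant up to 10% at month 6 (assumption), 1 − 0.9^(10/182.5) = 0.6% are lost by day 10 and 9.4% after; 1 − 0.9^0.5 = 5.1% are lost by month 3 and 4.9% after. Observed control endpoints at stake: 152/0.9 × 0.0942 = 15.9; 134/0.9 × 0.0487 = 7.2; 271/0.9 × 0.0487 = 14.7.
2. *Phenoconversion.* Under 7.1, a participant on a strong CYP2D6 inhibitor is a PM whatever the genotype, so could be classified without an assay. For chronic pain, 10.1 gives 10–15% actionable by genotype plus 20% by phenoconversion, so 20/35 to 20/30, or 57–67%, of the group is pheno-converted. Strong and moderate inhibitors are not split. If all were strong (assumption), 14.9 falls to between 14.9 × 10/30 = 5.0 and 14.9 × 15/35 = 6.4. If none were, 14.9 stands.

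**Bias.** Let drop-outs differ from completers by k SD on the primary endpoint. The documents give no value; k = 0, 0.25 and 0.5 are shown.

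(a) *Observed endpoints only, no imputation.* Bias = k × (lost after endpoint)/(1 − lost before endpoint): 0.0942/0.9942 = 0.0948 for acute pain and 0.0487/0.9487 = 0.0513 for the other two.

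(b) *Imputation fully restores the intervention mean while unclassified controls stay out.* Bias = 0.10 × k. This is the upper bound at 10% loss.

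Type 1 error by normal approximation at alpha 0.049, with intervention/control sizes 168/152, 141/134 and 286/271 for (a), and 152, 134 and 271 per arm for (b):

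| | k = 0 | k = 0.25: bias (SD), type 1 error | k = 0.5: bias (SD), type 1 error |
|---|---|---|---|
| (a) acute pain | 0, 0.049 | 0.024, 0.054 | 0.047, 0.070 |
| (a) chronic pain | 0, 0.049 | 0.013, 0.050 | 0.026, 0.054 |
| (a) depression | 0, 0.049 | 0.013, 0.052 | 0.026, 0.059 |
| (b) acute pain | 0, 0.049 | 0.025, 0.054 | 0.05, 0.071 |
| (b) chronic pain | 0, 0.049 | 0.025, 0.054 | 0.05, 0.068 |
| (b) depression | 0, 0.049 | 0.025, 0.059 | 0.05, 0.088 |

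A shift of 0.05 SD is 13%, 12.5% and 18% of the design effects (0.05/0.375, 0.05/0.40, 0.05/0.28). The 0.5 end is strong: at an assumed baseline to follow-up correlation of 0.5, with loss driven by baseline, drop-outs would have to be about 0.5/0.5 = 1 SD worse at baseline.

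**Power.** Table 9 already counts completers, so power stays near 90%. With 20% of controls ungenotyped and 10% lost in the intervention arm it is about 88–89%.

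**The case against.** The best defence is that the 7.5 sentence sets timing: it keeps control testing from happening too early and does not say that non-completers go untested. Other sections speak of time. The synopsis has "6-month delayed testing on participants receiving standard care (Control arm"; 10.1 speaks of a delay in the control arm; 10.7 says "the drug metabolizer phenotypes for participants in the Control arm is determined around the time of the 6-month follow up assessments". Where the authors wanted a completer restriction they wrote one, for the interim analysis. Fuller missing-data rules are deferred to separate SAPs, and storage and transport details to the MOP, none of which was available here.

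Much of this stands. A reader might infer that the plan removes control non-completers from the final analysis, or that the primary comparison is biased. The documents support neither: 10.3 sets no completion condition, and bias needs both the literal reading and a difference between drop-outs and completers that nobody has measured.

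What does not fall away is the gap. Section 7.5 is the instruction the laboratories follow and it names completion as the trigger. No section provides for testing a control who never completes, and the deferrals in 7.5 and 10.8 name neither the testing trigger nor membership of the primary set. Stretching the imputation rule in 10.8 to cover phenotype would be a guess.

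It is also fair to say that testing on the 6-month date itself would be a poor remedy. The assessment window is ±14 days (Table 8), results take about a week to reach the record (7.3) and go to providers (7.6), so a control surveyed late in the window could have results returned before the 6-month endpoints are collected.

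**Conclusion.** The point holds as an ambiguity in how the final primary set is formed in all three trials, with medium confidence because the unseen SAPs or MOP may resolve it. Under the literal wording, at most about 17, 15 and 30 actionable controls would be unclassified. These are ceilings, given phenoconversion and the need for an observed endpoint. Any bias is zero if drop-outs resemble completers and at most about 0.025 to 0.05 SD under the assumed 0.25 to 0.5 SD difference, direction unknown. The counts and bias bounds assume 10% loss by month 6; higher loss would raise them in proportion. It should be fixed because the remedy is cheap and the samples are already stored.

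**What to change.** **Section 7.5**, replace the control trigger with: *Each stored control sample is processed once the 6-month assessment is completed or the 6-month assessment window (+14 days) has closed, whichever comes first, unless consent for use of the sample was refused or withdrawn.* Testing then still follows collection of the 6-month endpoints.

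**Sections 10.3 and 10.8**, add: *The primary set does not depend on completing the 6-month assessment in either arm. Acute pain participants who never have surgery are handled the same way in both arms. The number randomised without a phenotype is reported by arm, and a sensitivity analysis applies the same phenotype-availability restriction (6-month completers) to both arms or multiply imputes phenotype.* The surgery sentence is needed because acute pain follow-up is timed from surgery (7.3), so a control without surgery has no 6-month window.

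**Cost.** Wording in the protocol and MOP, plus assays on stored samples for the 10% of controls lost:

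- synopsis totals: 865 × 0.93 × 0.10 + 492.5 × 0.10 + 770 × 0.10 = 80.4 + 49.3 + 77.0, about 207
- Table 9 totals: 1,010 × 0.93 × 0.10 + 497 × 0.10 + 754 × 0.10 = 93.9 + 49.7 + 75.4, about 219

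A few more control endpoints will need imputing. Some asymmetry remains where a control sample cannot be used, through refused or withdrawn consent or under 8.4: "If specimens or data have been stored as part of the research study, they too may be destroyed without participant consent". The report by arm and the sensitivity analysis cover that remainder. The MOP should also say how results are returned for controls lost to follow-up.
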